# **Overall Clinical Development Strategy**

The ultimate goal of the ETVAX vaccine clinical development plan is to demonstrate the safety and efficacy of this vaccine approach, with or without dmLT adjuvant, in a series of studies to gain sufficient information to achieve both local registration of the vaccine in the low income country(ies) where the pivotal trials will be conducted and prequalification by WHO to support product acquisition by GAVI, UNICEF or others for distribution, in general, to low income countries. Briefly, the overall clinical development plan consists of: 1) the first in human Phase I safety trial recently performed in Sweden; 2) the proposed Phase I/II descending age safety and immunogenicity trial in adults, children, toddlers and infants in Bangladesh; 3) an expanded phase II immunogenicity study in the target age group, as needed to further define the vaccine dose, inclusion of dmLT, schedule and age of administration, should the information obtained from the proposed trial be insufficient in that respect, especially should modifications be made to the current study product; and 4) Phase III efficacy trials to evaluate vaccine efficacy against moderate to severe ETEC diarrhea. Additional clinical trial evaluations could include: clinical assessment of lot-to-lot consistency (potentially could be combined with the efficacy trials); assessment of interference of the vaccine with the immune responses to routine EPI vaccinations; and assessment of vaccine safety and immunogenicity in other populations.

### **Research Design and Methods**

Describe the research design and methods and procedures to be used in achieving the specific aims of the research project. If applicable, mention the type of personal protective equipment (PPE), use of aerosol confinement, and the need for the use BSL2 or BSL3 laboratory for different part of the intended research in the methods. Define the study population with inclusion and exclusion criteria, the sampling design, list the important outcome and exposure variables, describe the data collection methods/tools, and include any follow-up plans if applicable. Justify the scientific validity of the methodological approach (biomedical, social, gender, or environmental).

Also, discuss the limitations and difficulties of the proposed procedures and sufficiently justify the use of them.

This is a single site, double-blind, randomized, placebo-controlled, dose-escalation, age-descending study that will start testing the vaccine in healthy adults, and move sequentially into toddlers, young children and infants. The study is designed as 4 parts. All participants will receive two doses of vaccine with or without dmLT adjuvant on an outpatient basis. Before moving to the next lower age group, available safety data will be evaluated and reviewed by the icddr,b Data Safety Monitoring Board (DSMB), after which they will make a recommendation whether to proceed to the next age group.

#### PART A: Adults (18-45 years, inclusive)

The first part (Part A) will enroll a total of 45 adult participants (30 vaccinees and 15 placebos) into one cohort. Approximately 45 participants will be randomized to receive two doses of ETVAX alone, (15 participants), ETVAX + 10 ug dmLT (15 participants), or placebo (15 participants) in a double blinded manner. ETVAX will be administered at full dose ( $10^{11}$  inactivated *E. coli* bacteria). The placebo preparation will be sodium bicarbonate buffer. Given a planned sample size of groups of 15 adults each receiving ETVAX with and without dmLT or placebo, Part A will have an approximately 90% chance of observing at least one serious adverse event or adverse event of special interest for events that occur at a rate of 15%. The number and allocation of participants in Part A are shown below.

CohortVaccine10 ug dmLT(N)Schedule						
	Full dose		15			
A1	Full dose	YES	15	Day 0, 14 $\pm 2$		
	Placebo		15			
ICDDR,B DSMB SAFETY REVIEW OF PART A						

#### PART A: Vaccine Dose and Participant Allocation By Cohort

Upon accumulation of all available safety data through Day 3 after the second immunization, the Independent Protocol Safety Team (IPST), comprised of three independent safety monitors, will convene and make a recommendation to the icddr,b DSMB whether to proceed to Part B. Independent safety monitors will be individuals not associated with study operations and who have clinical trials and infectious disease experience. Subsequently, the icddr,b DSMB will convene to review the same dataset and make a recommendation to the Sponsor whether to proceed to Part B. If dmLT is not tolerated in this age-group, it will not be carried forward and ETVAX will be tested alone in Parts B, C and D. Note: Reactogenicity will be assessed through 7 days post dose 1 and dose 2; however, only data through Day 3 after the second dose is needed for all IPST and DSMB reviews.

### PART B: Toddlers (2-4 years/24-59 months, inclusive)

The second part (Part B) will enroll a total of 150 toddlers (90 vaccinees and 60 placebos), age 2-4 years (24-59 months, inclusive) into six separate cohorts to be recruited step-wise. The first cohort (B1) will include 25 toddlers, randomized to receive two administrations of ETVAX at /4 dose (15 children) or placebo (10 children). The second cohort (B2) will include 25 toddlers, randomized to receive two administrations of ETVAX alone at /2 dose (15 children) or placebo (10 children). The third cohort (B3) will include 25 toddlers, randomized to receive two administrations of ETVAX alone at full dose (15 children) or placebo (10 children). The fourth cohort (B4) will include 25 toddlers, randomized to receive two administrations of ETVAX at the highest safe dose (either the full dose, /2 dose, or /4 dose) together with 2.5 ug dmLT (15 children) or placebo (10 children). The fifth cohort (B5) will include 25 toddlers, randomized to receive two administrations of ETVAX at the highest safe dose (either the full dose, /2 dose, or /4 dose) together with 5 ug dmLT (15 children) or placebo (10 children). The sixth cohort (B6) will include 25 toddlers, randomized to receive two administrations of ETVAX at the highest safe dose (either the full dose, /2 dose, or /4 dose) together with 5 ug dmLT (15 children) or placebo (10 children). The sixth cohort (B6) will include 25 toddlers, randomized to receive two administrations of ETVAX at the highest safe dose (either the full dose, /2 dose, or /4 dose) together with 5 ug dmLT (15 children) or placebo (10 children). The sixth cohort (B6) will include 25 toddlers, randomized to receive two administrations of ETVAX at the highest safe dose (either the full dose, /2 dose, or /4 dose) together with 10 ug dmLT

(15 children) or placebo (10 children). After each cohort, the IPST will review available safety data through Day 3 after the second immunization to make the recommendation to the Sponsor whether to proceed with the initiation of the next dose cohort. After Cohort B1, the DSMB will review available safety data through Day 3 after the second immunization to also make a recommendation to the Sponsor whether to proceed with the initiation of Cohort C1 (first dose cohort in 13-23 month old children). Given a planned sample size of groups of 15 toddlers each receiving varying doses of ETVAX with and without dmLT or placebo, Part B will have an approximately 90% chance of observing at least one serious adverse event of special interest for events that occur at a rate of 15%. The number and allocation of participants in Part B are shown below.

Cohort	Vaccine	dmLT	(N)	Schedule				
D1	 / 4 dose		15	$\mathbf{D} = 0.14 \pm 2$				
B1	Placebo		10	Day 0, $14 \pm 2$				
Independent Protocol Safety Team (IPST) reviews data through Day 3 after the second administration and makes a								
recommendation to the Sponsor whether to proceed to the initiation of Cohort B2; DSMB reviews the same dataset and makes a recommendation to the Sponsor whether to proceed to the initiation of Cohort C1.								
and makes a r		nsor whether to pro-		n of Cohort C1.				
B2	 / 2 dose		15	Day 0, $14 \pm 2$				
	Placebo		10					
			ation and makes a re	ecommendation to the Sponsor				
whether to pr	oceed to the initiation of Co	bhort B3.						
B3	Full dose		15	$Dot 0, 14 \pm 2$				
БЭ	Placebo		10	Day 0, $14 \pm 2$				
IPST reviews data through Day 3 after the second administration and makes a recommendation to the Sponsor of								
the highest safe dose and whether to proceed with the highest safe dose plus 2.5 ug of dmLT (Cohort B4).								
B4	Highest safe dose	2.5 ug	15	$D_{22} = 0.14 \pm 2$				
D4	Placebo		10	Day 0, $14 \pm 2$				
IPST reviews	data through Day 3 after th	e second administra	ation and makes a re	ecommendation to the Sponsor of				
the highest sa	fe dose and whether to proc	eed with the highes	st safe dose plus 5 u	g of dmLT (Cohort B5).				
D5	Highest safe dose	5 ug	15	$D_{11} = 0.14 \pm 2$				
B5	Placebo		10	Day 0, $14 \pm 2$				
IPST reviews data through Day 3 after the second administration and makes a recommendation to the Sponsor								
whether to proceed with the highest safe dose plus 10 ug of dmLT (Cohort B6).								
D4	Highest safe dose	10 ug	15	$D_{res} = 0.14 \pm 2$				
B6	Placebo		10	Day 0, $14 \pm 2$				
ICDDR,B DSMB SAFETY REVIEW OF PART B								

#### PART B: Vaccine Dose and Participant Allocation By Cohort

If dmLT is not tolerated in this age-group, ETVAX will be tested alone in Parts C and D (i.e., cohorts C3, C4, D4 and D5 will be dropped). Note: Reactogenicity will be assessed through 7 days post dose 1 and dose 2; however, only data through Day 3 after the second dose is needed for all IPST and DSMB reviews.

PART C: Younger children (12-23 months, inclusive)

The third part will enroll a total of 100 participants. The first cohort (C1) will include 25 children, randomized to receive two administrations of ETVAX alone at ¼ dose (15 children) or placebo (10 children). The second cohort (C2) will include 25 children, randomized to receive two administrations of ETVAX alone at ½ dose (15 children) or placebo (10 children). The third cohort (C3) will include 25 children randomized to receive two administrations of ETVAX at the highest safe dose (either ½ or ¼ dose) together with 2.5 ug dmLT (15 children) or placebo (10 children). The fourth cohort (C4) will include 25 children randomized to receive two administrations of ETVAX at the dose evaluated in C4 (either ½ or ¼ dose) together with 5 ug dmLT (15 children) or placebo (10 children). After each cohort, the IPST will review available safety data through Day 3 after the second immunization to make the recommendation to the Sponsor whether to proceed with the initiation of the next dose cohort. After Cohort C1, the DSMB will review available safety data through Day 3 after the second immunization to the Sponsor whether to proceed with the second immunization to also make a recommendation to the Sponsor whether to proceed with

the initiation of Cohort D1 (first dose cohort in infants). Given a planned sample size of groups of 15 children each receiving varying doses of ETVAX with and without dmLT or placebo, Part C will have an approximately 90% chance of observing at least one serious adverse event or adverse event of special interest for events that occur at a rate of 15%. The number and allocation of participants in Part C are shown below.

Cohort	Vaccine	dmLT	(N)	Schedule	
Cl	 / 4 dose		15	$D_{1} = 0.14 \pm 2$	
C1	Placebo		10	Day 0, $14 \pm 2$	
whether to pr	data through Day 3 after the se oceed to the initiation of Cohor whether to proceed to the initiati	t C2; DSMB reviews th			
C2	 / 2 dose		15	$D_{\text{ext}} = 0.14 \pm 2$	
C2	Placebo		10	Day 0, $14 \pm 2$	
	data through Day 3 after the se fe dose and whether to proceed				
C3	Highest safe dose	2.5 μg	15	$D_{ext} = 0.14 \pm 2$	
0.5	Placebo		10	Day 0, $14 \pm 2$	
	data through Day 3 after the se oceed with the highest safe dos			ation to the Sponsor	
C4	Highest safe dose	5 µg	15	$D_{av} = 0.14 \pm 2$	
C4	Placebo		10	Day 0, $14 \pm 2$	
ICDDR,B DS	SMB SAFETY REVIEW OF PA	ART C			

If dmLT is not tolerated in this age-group, ETVAX will be tested alone in Part D (i.e., cohorts D4 and D5 will be dropped). Note: Reactogenicity will be assessed through 7 days post dose 1 and dose 2; however, only data through Day 3 after the second dose is needed for all IPST and DSMB reviews.

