# Methods:

This is a single site, Phase I/II, double-blind, randomized, placebo-controlled, dose-escalation, age-descending study that will first test the vaccine with and without dmLT in healthy adults, and then move sequentially into toddlers (24-59 months old), younger children (12-23 months old) and infants (6-11 months old). The study is designed as 4 parts, one for each of the four age-groups. All participants will receive two oral doses of ETVAX with or without dmLT adjuvant or placebo, with different vaccine dose levels assessed within each age-group. Before moving to higher dose levels, available safety data will be evaluated and reviewed by an Independent Protocol Safety Team (IPST) comprised of three independent safety monitors, who will review available safety data through Day 3 after the second immunization to make the recommendation to the Sponsor whether to proceed with the initiation of the next dose cohort in that same age group. Independent safety monitors will be individuals not associated with study operations and who have clinical trials and infectious disease experience. Before moving to the next lower age group, the icddr,b Data Safety Monitoring Board (DSMB) will review all

available safety data through Day 3 after the second immunization to make the recommendation to the Sponsor whether to proceed with initiation of the first dose cohort in an age group.

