### Studies in endemic areas

In Phase I/Phase II studies in Egypt, in which the rCTB-CF ETEC vaccine was evaluated in an age-descending manner starting with adults and subsequently in children, 6-12 years, 2-4 years, and 6-18 months of age, the vaccine was found to be safe and immunogenic in all age groups when given in two or three doses two weeks apart [29, 30]. However, when tested for protection in an active surveillance phase III study in 6-18 month old children the vaccine only provided a non-significant, 20%, protective efficacy against mild/moderate disease. No cases of severe (dehydrating) diarrhea occurred during the study period [33].

When testing of the vaccine in parallel age-descending studies in Bangladesh, it was found to be well tolerated [29] except in the youngest age group (6-17 months) in which increased frequency of vomiting was observed [32]. The vaccine was immunogenic in all age groups, although responses in infants were lower than in older children. Based on the side-effects observed in the youngest age-group a dose-finding study was conducted in children 6-17 months of age who were given

full, half and quarter dose of vaccine; when given in a quarter dose the vaccine was still immunogenic and adverse events in the form of vomiting was only seen in 4% of the vaccinated children and in 2.5 % of the placebo recipients [32].

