#### Safety Oversight

A Data and Safety Monitoring Board (DSMB) will be formed by the Ethical Review Committee to evaluate and assess the safety of study participants. In addition, an Independent Protocol Safety Team (IPST) formed for the study will carry out the safety and clinical evaluation at the icddr,b. Moreover, there will be a team comprising of the study physician, the Medical Monitor from EMMES, the principal investigator, and the Medical Officer from PVS for evaluation of the study at different intervals in the study.

Before enrolling participants in subsequent cohorts within an age group, the safety data from the previous cohort(s) will be evaluated and reviewed by the IPST. These data include, but are not limited to, physical examinations, vital signs, and solicited reactogenicity symptoms. The IPST will convene after each cohort within an age group to review data through Day 3 after the second vaccine administration and make a recommendation to the Sponsor on whether to proceed to the initiation of the following cohort.

The DSMB will be composed of 3-4 members, two of which are nominated by the ERC chairperson. The PI also has the option of nominating 1-2 members with therapeutic expertise. The DSMB meets before study initiation, prior to age deescalation, and after the study closeout. The PI can also request a DSMB meeting depending upon the study complexity or in light of safety concerns. The DSMB will advise the PI of its findings and provide recommendations. The DSMB will review all unanticipated problems involving risk to the participants or others, serious adverse events, and all participant deaths associated with the protocol. The PI will inform the EMMES Medical Monitor and the PVS Medical Officer in detail about the discussions of those meetings.

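### In the protocol's text, half dose at 12-23 months (C2) can open before the scheduled half-dose review in toddlers (B2) is complete, because C2 waits only for C1

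*Protocol*

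**What the plan says.** The allocation table for Part B attaches two decisions to the B1 data (quarter dose, toddlers). The independent safety team (IPST) recommends whether "to proceed to the initiation of Cohort B2; DSMB reviews the same dataset" and recommends on C1 (quarter dose, 12-23 months). After B2 (half dose, toddlers), the table names one decision only, the opening of B3.

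In Part C, "The second cohort (C2) will include 25 children, randomized to receive two administrations of ETVAX alone at ½ dose". Its release rule is the general one: "After each cohort, the IPST will review available safety data through Day 3 after the second immunization to make the recommendation to the Sponsor". The row between C1 and C2 in the Part C table names the C1 review and no other.

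The general sections do not add a link from B2 to C2. In the Methods summary, the DSMB's review across age groups decides "whether to proceed with initiation of the first dose cohort in an age group", so it covers C1 and not C2. Safety Oversight frames the other review by age group: "Before enrolling participants in subsequent cohorts within an age group, the safety data from the previous cohort(s) will be evaluated and reviewed by the IPST".

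One tolerability finding is carried down to younger groups in writing, and it concerns the adjuvant: "If dmLT is not tolerated in this age-group, ETVAX will be tested alone in Parts C and D". There is no matching sentence for an ETVAX dose level that toddlers do not tolerate.

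**The concern.** In a trial that escalates dose and descends in age, one expects a dose to be reviewed in the older group before it is given to the next younger one. The text secures this for quarter dose (B1 before C1) but not for half dose (B2 before C2).

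The protocol's own history shows why the order matters. Under Studies in endemic areas, the first-generation vaccine was well tolerated in Bangladesh "except in the youngest age group (6-17 months) in which increased frequency of vomiting was observed", and the Scientific Rationale links the problem to high doses. That age band overlaps the lower half of Part C. At quarter dose, "adverse events in the form of vomiting was only seen in 4% of the vaccinated children", against 2.5% on placebo. No figure is given for half dose, and these data concern a different product. Adult data at full dose therefore do not settle how half dose is tolerated in small children.

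At stake is whether a pattern of frequent mild or moderate vomiting at half dose in toddlers would be formally judged before younger children receive that dose. The count-based pause criteria look at grade 3 or worse. A pattern of grade 1-2 vomiting would have to be picked up by judgement, and the scheduled B2 review is the natural place for that.

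**Working it through.** **Release chain, from the Part B and Part C tables**

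| Data reviewed | Dose and age | Releases |
|---|---|---|
| B1 | quarter, 24-59 months | B2 (IPST) and C1 (DSMB) |
| C1 | quarter, 12-23 months | C2 (IPST) and D1 (DSMB) |
| B2 | half, 24-59 months | B3 (IPST) |

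No row leads from B2 to C2.

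**Exposure in C2.** 15 vaccinees x 2 doses = 30 administrations. Half dose divided by quarter dose = 2, so C2 receives twice what was reviewed in B1 and C1.

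**What a cohort of 15 can show.** The Part C text gives about a 90% chance of seeing at least one event at a true rate of 15%. Check: 1 - 0.85^15 = 0.913, which agrees. At the rates in the Sample Size Calculation: 1 - (1 - 0.143)^15 = 0.901 and 1 - (1 - 0.103)^15 = 0.804. A completed B2 review would thus usually reveal a common reaction to half dose in toddlers. These figures describe toddlers; they do not measure added risk in C2.

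**When the order can reverse.** B2 and C1 have the same size (25 children, 15 vaccinees) and the same read-out after a child's first dose: 14 + 3 = 17 days, or 12 + 3 = 15 to 16 + 3 = 19 with the visit window. Let E be the days needed to accrue a cohort and L the days by which C1 opens after B2. Counting from the opening of B2:

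- B2 data complete: E(B2) + 17
- C1 data complete: L + E(C1) + 17
- C1 is ready first if E(B2) - E(C1) > L
- Wait for C2 if it must also await B2: max(0, E(B2) - E(C1) - L)

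The protocol states neither E nor L. Assuming accrual of 7, 14 or 28 days and L of 0, 7 or 14 days, the wait in days is:

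| E(B2), E(C1) | L = 0 | L = 7 | L = 14 |
|---|---|---|---|
| 28, 7 | 21 | 14 | 7 |
| 28, 14 | 14 | 7 | 0 |
| 14, 7 | 7 | 0 | 0 |
| B2 no slower than C1 | 0 | 0 | 0 |

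The visit window can shift these by up to 19 - 15 = 4 days. If C1 opened before B2, L would be negative and the wait would grow by a day for each day of that head start.

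**The case against.** The strongest reply has four parts.

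1. **The figure.** The end of the Part D section points to a figure with the dosing and escalation schedule, which is where an ordering across age groups would be drawn. It was not available for this review. A reader might infer that the trial has no such gate at all. The documents do not support that; the point is confined to the text.

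2. **Same-age evidence comes first.** C2 opens on 30 reviewed quarter-dose vaccinees (15 in B1, 15 in C1) and 30 reviewed adults at full dose, which is more than B2 has when it opens at the same dose. Toddlers of 24-59 months also lie outside the band where vomiting was seen, so a clean B2 review would not clear half dose at 12-17 months. This is fair, but it works in one direction only. A bad result in toddlers would be a reason not to give the dose to younger children.

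3. **Other safeguards.** The IPST reviews both Parts and works from the data at hand, so partial B2 data can inform the C2 decision. Reactogenicity is reviewed weekly (Notifications and Review). At most five participants are dosed on a cohort's first day (Preparation and Administration). Study Pause and Study Pause Procedure let any safety concern lead to a halt, raised by any IPST or DSMB member among others. A reader might infer that milder reactions in B2 could not stop C2 because the count-based criteria require grade 3. These provisions show otherwise. They lower the risk, but all rest on discretion, and none requires the B2 review to be finished.

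4. **Narrow timing.** Cohort size and read-out are equal, and in Part A the DSMB meets after the IPST. If that order also held after B1, C1 would open no earlier than B2. A reader might infer that C2 will precede the B2 review; the text only permits it.

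A reader might also extend the point to half dose in infants (D3). D3 follows the D1 and D2 reviews, so C2 would normally have been reviewed by then. The omission there is formal only.

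**Conclusion.** The point holds for the text. C2 is released on C1 alone, B2 runs alongside C1, and no sentence makes a completed half-dose review in toddlers a condition for half dose at 12-23 months. The reversal requires B2 to accrue more slowly than C1 by more than C1's opening lag, and the protocol gives no accrual times from which to judge how likely that is. If it happens, up to 15 vaccinees and 30 administrations are affected, with several discretionary safeguards still in place. The risk is low. This is a cheap improvement of low-to-moderate priority, subject to what the escalation figure shows.

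**What to change.** In the Part B and Part C descriptions, and in the matching table rows, state that C2 opens only after the IPST has reviewed both C1 and B2 to Day 3 after dose 2 and has found half dose acceptable in toddlers. If the escalation figure already shows this order, bring the text into line with it.

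The cost is a sentence or two and no extra meeting, since B2 is already reviewed before B3. C2 may wait for B2 when B2 lags: 0 to 21 days under the assumptions above, and nothing when B2 accrues no slower than C1 and opens no later. If half dose is not found acceptable and C2 does not open, C3 can still proceed, because the Part C text already allows quarter dose there.
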